## 10. EXPERIMENTAL PLAN

### 10.1 OVERVIEW

This study will be conducted in accordance with U.S. Code of Federal Regulations the Declaration of Helsinki, ISO 14155:2020 and all other applicable laws and regulations. The study will not begin until IRB/IEC approval has been obtained.

This study will be a prospective, three-arm, randomized, controlled clinical study conducted at up to 20 study sites located in North America. [REDACTED]

[REDACTED] After informed consent is obtained and all eligibility criteria are confirmed as being met, the subject (one or both eyes) may be enrolled and randomized to a treatment group.

For subjects with both eyes eligible, the investigator will choose which eye to operate on first at his/her discretion and standard clinical practice (e.g., the eye with the worse cataract, poorer best corrected distance vision and/or more severe optical/visual complaints); both eyes will be implanted with the same lens model. [REDACTED]

The study visits and procedures will include procedures that are study-specific or part of normal clinical practice, [REDACTED]

[REDACTED] The operative visit procedures for the study will be standard procedures for cataract surgery and IOL implantation.

Key postoperative assessments include IOL axis measurement [REDACTED]

[figure not shown]
### 10.2 VISIT SCHEDULE

The study visit schedule for all study subjects is outlined in [TABLE 1](#).

Each subject is intended to have unilateral or bilateral cataract surgery with the lens model assigned by randomization. [REDACTED]

[REDACTED] Unscheduled visits may be conducted as necessary at the discretion of the investigator for medically indicated follow-up.

**TABLE 1: Visit Schedule**

**10.3 PREOPERATIVE PROCEDURES**

All subjects enrolled in the study must sign the current IEC/IRB-approved ICF and meet the eligibility criteria. The ICF must be signed before any study-specific examinations are performed, and this must be documented in the source documents.

An Authorization for Use/Disclosure of Health Information Form (HIPAA authorization) or similar medical treatment privacy law documentation must also be signed. The preoperative procedures

will follow the normal clinical practice. [REDACTED]  
[REDACTED]  
[REDACTED]  
[REDACTED]  
[REDACTED]  
[REDACTED]  
[REDACTED]  
[REDACTED]  
[REDACTED]  
[REDACTED]

[REDACTED]  
[REDACTED]  
[REDACTED]  
[REDACTED]

**Preoperative testing:** to be performed for each enrolled eye includes the following:

POTENTIAL POSTOPERATIVE DISTANCE VISUAL ACUITY

The subject must be capable of achieving Snellen 20/32 or better best-corrected distance vision in each eye after cataract extraction and IOL implantation. [REDACTED]  
[REDACTED]  
[REDACTED]

BEST-CORRECTED DISTANCE VISUAL ACUITY AND MANIFEST REFRACTION

Manifest refraction should be performed on each study eye to obtain monocular BCDVA using logMAR visual acuity charts. Monocular BCDVA must be worse than 20/40 Snellen (0.3 logMAR) to be considered eligible to participate in the study.

KERATOMETRY

Corneal astigmatism is to be measured by keratometry or topography. Predicted postoperative corneal astigmatism, based on measurements by keratometry, should be less than 1.00 D. No irregular astigmatism should be present preoperatively. [REDACTED]  
[REDACTED]  
[REDACTED]  
[REDACTED]

CONTACT LENS WEAR AND CORNEAL STABILITY

The surgeon should follow their routine procedures to establish keratometric corneal stability in contact lens wearers before surgery.  
[REDACTED]  
[REDACTED]

[REDACTED]

IOL POWER AND TARGETED REFRACTION

The spherical equivalent lens power, as determined by the investigator's standard biometry methods, [REDACTED]

[REDACTED]

[REDACTED]

ADDITIONAL PREOPERATIVE INFORMATION COLLECTED SHOULD INCLUDE:

- Informed consent
- Subject demographic information
- Planned surgery dates for each enrolled eye
- Ocular history, including presence of ocular pathology for each enrolled eye
- [REDACTED]
- Any medical findings from a slit lamp exam, dilated fundus exam, intraocular pressure or other assessment.
- Ocular and systemic medications

**10.4 SELECTION OF IOL POWER**

In order to facilitate IOL selection and axis placement, JJSV provides a web-based proprietary tool, the TECNIS Toric Calculator ([www.TecnisToricCalc.com](http://www.TecnisToricCalc.com)) for the surgeon. [REDACTED]

[REDACTED]

[REDACTED]

**10.5 RANDOMIZATION AND MASKING**

A randomization list will be created by the JJSV biostatistician for each investigative site. Subjects will be randomized to either the test #1, test #2, or control IOL on a 1:1:1 basis. Randomization will take place after the subject has signed the informed consent document, has met all inclusion and exclusion criteria, and the investigator has documented which eye will be the first implanted (if bilaterally enrolled).

As part of the informed consent process, the investigator or delegate will explain to the subject the requirements of a randomized study and the differences expected between the test and control lenses. Once the investigator has determined that a subject is eligible for inclusion in the study and documented which eye will be implanted first (if bilateral), the site will proceed with the randomization. After notification, the site will open the next sealed randomization envelope in numerical order to determine lens group assignment. The randomization envelope number will be recorded on the Operative Case Report Form.

[REDACTED]

The subjects and the study technicians performing the postoperative vision tests are to be masked through study completion. [REDACTED]

[REDACTED]

[REDACTED]

[REDACTED]

## 10.6 STUDY LENS SUPPLY

[REDACTED]

## 10.7 OPERATIVE PROCEDURES

Surgical procedures should be in accordance with each site's routine practice and in accordance with the product labeling. The surgeons should follow the procedures as described in the respective IOL's Directions for Use to ensure appropriate alignment of the IOL axis.

[REDACTED]

### REFERENCE AXIS

Prior to surgery the operative eye should be marked per the surgeon's routine method.

Operative case report forms should include the following information:

### INCISION TYPE AND SIZE

The incision may be clear corneal, limbal or scleral tunnel at the discretion of the investigator. Lenses should be inserted per the investigator's standard technique when using the JJSV-qualified implantation system.

### BALANCED SALT SOLUTION (BSS) STERILE IRRIGATING SOLUTION

BSS solution should be used as is customary for each investigator and recorded on the case report form.

### VISCOELASTIC

Viscoelastic materials should be used as is customary for each investigator and recorded on the case report form (CRF).

### IMPLANT INSTRUMENTATION USED

[REDACTED] IOLs should be folded for implantation and inserted into the capsular bag using the TECNIS Simplicity Delivery System (preloaded).

[REDACTED]

[REDACTED] or any other insertion system qualified for use by the JJSV.

### BASELINE LENS AXIS

At the end of each case, the axis of lens in its final position should be recorded.

### SURGICAL COMPLICATIONS

Should a surgical complication occur, implantation of a study lens will be at the investigator's discretion. The subject should be exited from the study if a non-study lens is implanted as a result of a surgical complication during implantation; however, the eye will be followed until resolution of the complication prior to exiting the subject.

### MEDICATIONS

Preoperative, operative and intraoperative medications should be used as is customary for each investigator and recorded in the source document for each subject, as appropriate. [REDACTED]

### TYPE OF CLOSURE

Wound closure is left to the surgeon's discretion and will be recorded on the CRF.

### ADDITIONAL OPERATIVE INFORMATION THAT MAY BE COLLECTED:

- Date of surgery
- Operative eye
- Lens power and serial number
- Intended residual spherical equivalent
- Intended residual cylinder
- Surgical complications or other surgical procedures
- Product complaints
- Serious and/or device-related adverse events

## 10.8 POSTOPERATIVE PROCEDURES

Postoperatively, subjects will be examined according to the schedule in **Section 10.2**, Visit Schedule.

[REDACTED]

The postoperative CRF will be used to collect postoperative information, as following (not all data are required at every visit):

[REDACTED]

[REDACTED]

[REDACTED]

[REDACTED]

[REDACTED]

[REDACTED]

[REDACTED]

[REDACTED]

[REDACTED]

[REDACTED]

[REDACTED]

[REDACTED]

[REDACTED]

[REDACTED]

[REDACTED]

[REDACTED]

[REDACTED]

### ADVERSE EVENTS

Subjects should be assessed at each visit for occurrence of and/or change in status of any adverse events, particularly serious and/or device-related adverse events, and secondary surgical interventions. [REDACTED]

[REDACTED]

### Secondary Surgical Interventions

Secondary surgical interventions due to refractive error and/or medical complications are considered serious adverse events. Secondary surgical interventions that occur under the circumstances below will be considered device-related serious adverse event/device effects:"

- IOL repositioning due to a significant axis misalignment resulting in a visual outcome that is unsatisfactory, providing the axis misalignment is rotationally correctable.
- IOL exchange due to incorrect spherical power resulting in a significant decrease in uncorrected visual acuity.
- IOL exchange due to surgical or postoperative medical complications or adverse events.

If IOL repositioning procedure is required, the investigator should document the IOL position (including axis measurement) prior to repositioning procedures. After repositioning, the eye should be followed through study completion for safety. If a toric IOL is exchanged for a non-toric IOL, the subject should be followed until resolution of the serious adverse event/adverse device effect.

### **10.9 EXIT OF SUBJECTS**

An Exit CRF will be completed for each subject that completes the study or exits the study before completing all scheduled visits.

A subject will be considered a "screen failure" if he/she does not meet the eligibility criteria, consent is withdrawn prior to surgery, implantation in the first eye is aborted due to a surgical complication, or the subject dies prior to first-eye treatment.

[REDACTED]

[REDACTED]

[REDACTED]

Subjects will be "discontinued" from the study if the subject does not undergo surgery; or if both study lenses are removed; or if the subject dies.

If a subject receives at least one study lens, he/she is to be followed according to the study procedures scheduled in **TABLE 1 (Section 10.2)**.

Subjects will be considered "lost-to-follow-up" from the study if there is no information to account for missing data or failing to complete the [REDACTED] study visit.

If a subject is exited early from the study, the investigator must indicate the reason for study exit on the CRF. In the event of a lens removal or other serious adverse event, the subject may be exited from the study; however, effort must be made by the investigator to follow the subject until resolution of the adverse event before exiting the subject from the study.

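### Protocol 10.9 calls a subject whose first-eye implantation is aborted a 'screen failure' although that subject is already randomised, and no visible table counts such subjects by assigned lens

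*Protocol*

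**What the plan says.** **Order of events.** Protocol 10.1 states that once consent is given and "all eligibility criteria are confirmed as being met, the subject (one or both eyes) may be enrolled and randomized to a treatment group". Protocol 10.5 agrees: "Randomization will take place after the subject has signed the informed consent document, has met all inclusion and exclusion criteria". It continues that "the site will open the next sealed randomization envelope in numerical order to determine lens group assignment". SAP 1.4 repeats this order. On recording, Protocol 10.5 says: "The randomization envelope number will be recorded on the Operative Case Report Form".

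**Exit labels (Protocol 10.9).** 'Screen failure' covers failed eligibility, consent withdrawn before surgery, and the cases where "implantation in the first eye is aborted due to a surgical complication, or the subject dies prior to first-eye treatment". 'Discontinued' covers subjects who do not have surgery, who have both study lenses removed, or who die.

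**Non-study lens after a complication.** Protocol 10.7 (Surgical Complications) says: "The subject should be exited from the study if a non-study lens is implanted as a result of a surgical complication during implantation". It adds that "the eye will be followed until resolution of the complication prior to exiting the subject". Protocol 10.9 says: "If a subject receives at least one study lens, he/she is to be followed according to the study procedures scheduled in" Table 1.

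**Population and tables.** The one visible population, All Implanted Safety (Protocol 21.1, SAP 2.1), takes randomised subjects who received a study lens and groups them by the lens received. SAP section 3 plans three outputs: enrolled subjects by site, accountability by scheduled visit, and a by-IOL table of available eyes with missing and active subjects. SAP 5 plans a listing of serious and device-related adverse events. Protocol 21.3 plans proportions of eyes with findings or adverse events by lens group, without a visible statement of the denominator.

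**The concern.** A screen failure is someone who never entered the randomised comparison. A surgical complication that stops implantation occurs after the envelope is opened and could depend on the lens or its delivery system. Labelling it a screening event moves the subject out of the randomised accounting.

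The visible plan does not bring the subject back. A subject with no study lens has no received-lens group, so only a count by assigned lens can show that subject, and none is named. The SAP is restricted to descriptive summaries after early termination, so the tables are the result. A reader comparing three lenses would want to know how many randomised subjects in each group ended without the lens, and why.

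**Working it through.** The documents state no figure on this point, so there is nothing to reproduce. The check compares the passages and then gives a rough scale.

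**Step 1: is the subject randomised?** Consent and eligibility come first, then the choice of first eye (if bilateral), then the envelope, then surgery (Protocol 10.1, 10.5; SAP 1.4). Anyone whose first-eye implantation is under way has an assigned lens. Protocol 10.9 does not say 'randomised'; that follows from this order.

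**Step 2: is the subject in the visible population?** Not if no study lens was implanted (Protocol 21.1, SAP 2.1).

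**Step 3: does a visible table count the subject by assigned lens?**

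| SAP section 3 output | Broken down by | Randomised, attempted or aborted named? |
|---|---|---|
| Enrolled subjects | Site | No |
| Accountability | Scheduled visit | No |
| Available eyes; missing and active subjects | IOL | No |

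SAP section 3 shows no redaction in the text supplied.

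**Step 4: are the labels exclusive?** Consent withdrawn or death before surgery fits 'screen failure'. Each also fits 'discontinued', as a subject without surgery or a death.

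**Step 5: do 10.7 and 10.9 agree?** Take a subject with a study lens in one eye and, after a complication, a non-study lens in the other. Protocol 10.7 exits the subject after the complication resolves. Protocol 10.9 keeps the subject on the visit schedule. Both apply.

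**Step 6: scale.** All inputs are assumed: n attempted eyes per arm, p the complication rate per attempted eye, k the share of complicated eyes that still receive the study lens. Eyes are treated as independent.

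Expected uncounted eyes per arm = n × p × (1 − k). For n = 30:

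| p | k = 0.8 | k = 0.6 | k = 0.4 |
|---|---|---|---|
| 1% | 0.06 | 0.12 | 0.18 |
| 3% | 0.18 | 0.36 | 0.54 |
| 5% | 0.30 | 0.60 | 0.90 |

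Example: 30 × 0.03 × (1 − 0.6) = 0.36.

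Probability that at least one of three arms has an uncounted eye = 1 − (1 − p(1 − k))^(3n), with 3n = 90:

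- p = 1%: 16%, 30% and 42% for k = 0.8, 0.6 and 0.4.
- p = 3%: 42%, 66% and 81%.

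At n = 100 and p = 3% the expected loss is 0.6, 1.2 and 1.8 eyes per arm, so the below-one-eye statement belongs to small arms.

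**The case against.** **Redaction.** Lines are blacked out directly after the screen-failure sentence in 10.9, around Protocol 21.1 and 21.3, and in the adverse event part of SAP 5. SAP 2.2 allows for more than one safety population. A further population, a table, or a boundary between the two exit labels may stand there. This limits the reporting point to what is visible and makes the table conditional. It does not rescue the label for an aborted implantation, because the order of randomisation and the label are both in clear text.

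**Events are captured.** Adverse events go on the case report form (Protocol 11.3), the eye is followed until the complication resolves (10.7), the exit reason is recorded (10.9), and SAP 5 lists serious and device-related events with no visible restriction to implanted eyes. This stands. What is left is the arm-level count, plus complications judged neither serious nor device-related, which that listing does not name.

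**Accountability by visit may help.** If the operative visit is a row in that table, some attrition would appear. The contents of Table 1 are not visible, and that output is not described as split by assigned lens.

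**A stronger reading.** A reader might infer that complication rates are biased between lenses. If proportions use implanted eyes only, the rate shown is pk/(1 − p + pk). At p = 3% and k = 0.6 this is 0.018/0.988 = 1.8%. The arithmetic is right, but the documents do not support the inference. They give no p, k or n, do not visibly state the base of the proportions, and promise no rate per attempted eye. The objective in SAP 1.1 concerns implanted eyes, so the All Implanted summary is a legitimate choice.

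**Conclusion.** The concern holds as a labelling and accountability defect of low importance. Protocol 10.9 treats a post-randomisation surgical event as a screening event, and the visible tables would not show how many randomised subjects per lens ended without a study lens.

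The expected loss stays below one eye per arm at 30 attempted eyes per arm, for assumed complication rates up to 5% and at least 40% of complicated eyes still implanted. No hypothesis test is affected, since reporting is descriptive only. It is not shown that any eye was lost from the count or that any lens comparison is distorted.

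The overlap between 'screen failure' and 'discontinued' is real in the visible text, though redacted lines in 10.9 may separate the two. The conflict between 10.7 and 10.9 over a subject with mixed lenses is a separate wording conflict.

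**What to change.** 1. In Protocol 10.9, or by a definition in SAP section 3, reserve 'screen failure' for subjects not randomised. Classify the others as 'randomised, not implanted', with the reason. Remove the overlap with 'discontinued' for consent withdrawal or death before surgery, unless redacted text in 10.9 already does so.
2. In SAP section 3, add one disposition table by assigned lens: subjects randomised, and eyes attempted (surgery started), aborted with reason, and implanted. Omit this if redacted text already provides it.
3. Reconcile Protocol 10.7 with 10.9 for a subject with a study lens in one eye and a non-study lens in the other after a complication.

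A row of operative complications per attempted eye, beside the All Implanted summary, is an optional supplement and does not correct an error.

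**Cost.** One extra table and some wording, with no new visits or tests. The inputs are largely foreseen: envelope number on the operative form, exit reason, and adverse events on the case report form. For a subject randomised who never reached surgery, the assignment may have to come from the opened envelope, since the operative form is the only visible place where its number is recorded. Because the study is ending early, the SAP table is the part that can still change the report.

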#### **10.10 UNSCHEDULED VISITS**

During the study period, if a non-protocol-required visit is done for the purpose of medically indicated follow-up for a study eye, data from this visit should be reported using the Unscheduled Visit CRF. The need for unscheduled visits is at the investigator's discretion. Specific examinations to be performed at unscheduled visits are also at the discretion of the investigator (based on the reason for the unscheduled visit) and data are to be recorded in the appropriate section of the CRF.

[REDACTED]

[REDACTED]

[REDACTED]

[REDACTED]

Conditions found postoperatively, but previously documented at the preoperative visit, do not trigger an unscheduled visit report. However, if the severity of the condition increases from the preoperative visit, an Unscheduled Visit CRF is needed.

#### **10.11 PROTOCOL DEVIATIONS**

Any departure from the protocol procedures represents a protocol deviation. Protocol deviations may be subject-based (e.g., inclusion/exclusion criteria, informed consent deviation, etc.) or procedural-based (e.g., out-of-interval visits, non-compliance with testing procedures, etc.). All protocol deviations will be documented in the Clinical Trial Management System. Any deviation made to protect the life or physical well-being of a subject in an emergency must be reported to JJSV within 5 working days. Protocol deviations will be monitored by the Sponsor, and if the non-

compliance is persistent or egregious, Sponsor may take action, including but not limited to termination of the investigator's participation in the study. The investigator is also responsible for informing the reviewing IEC of protocol non-compliance in accordance with the IEC requirements.

## **11. ADVERSE EVENTS AND PRODUCT COMPLAINTS**

### **11.1 ADVERSE EVENT DEFINITIONS**

#### **Adverse Event (AE)**

An adverse event is defined (per ISO 14155) as any untoward medical occurrence, unintended disease or injury, or untoward clinical signs (including abnormal laboratory findings) in subjects, users or other persons, whether related to the study device.

#### **Serious Adverse Event (SAE)**

An adverse event is considered serious (per ISO 14155) if it is an untoward occurrence which may or may not be related to use of the study device that

- is sight- or life-threatening,
- results in death,
- requires inpatient hospitalization or prolongation of hospitalization (a planned hospitalization for a pre-existing condition without a serious deterioration in health is not considered a serious adverse event),
- results in permanent impairment of a body structure or body function,
- necessitates medical or surgical intervention to prevent permanent impairment to a body structure or function, or
- results in fetal distress, fetal death or a congenital abnormality or birth defect including physical or mental impairment

#### **Device-Related Adverse Event/Adverse Device Effect (ADE)**

A device-related adverse event is defined as any adverse event that is believed to be definitely, probably, or possibly related to the study device (following the guidelines in Section 11.4, Causal Relationship). A device-related event is also considered an adverse device effect (ADE; following ISO 14155) resulting from the use of the study device that may result from user error, insufficiencies or inadequacies in the instructions for use, deployment, implantation, installation, operation or any malfunction of the device.

#### **Anticipated Study-Specific Serious Adverse Events**

The following is a list including, but not limited to, ocular serious adverse events that are anticipated and must be reported to JJSV for this study. Any events that are unlikely but anticipated (i.e., endophthalmitis) will be reported to the FDA and other appropriate regulatory agencies.

- Endophthalmitis/intraocular infection

- Hypopyon
- Hyphema
- IOL dislocation
- Cystoid macular edema
- Pupillary block
- Retinal detachment/tear
- Acute corneal decompensation
- Corneal edema accompanied by BCDVA of 20/40 (0.3 logMAR) or worse at 3 months or later
- Chronic anterior uveitis/iritis that persists at 3 months postoperative
- Raised IOP that persists (i.e., is present at 3 months postoperative or later)
- Toxic anterior segment syndrome
- Visual symptoms requiring secondary surgical intervention (e.g., lens removal)
- Tilt and decentration requiring secondary surgical intervention (e.g., repositioning)
- Residual refractive error resulting in a secondary surgical intervention
- Retained lens material resulting in secondary surgical intervention

**NOTE 1:** Wound “burps” during the first week after surgery, suture removal, planned blepharoplasty, and Nd:YAG capsulotomy (for PCO) are not considered adverse events for this study.

**NOTE 2:** Raised IOP requiring treatment, cornea edema, and iritis will only be considered serious if persistent at 3 months or later or sight-threatening at the time of occurrence. Treatment merely to hasten the resolution of such conditions (and not intended to prevent permanent damage to the eye) will not be reported as serious adverse events.

